Among AF patients with guideline indications for OAC for stroke prevention who have not received any OAC dispensing for at least one year, an education intervention at the patient-level and the provider-level will increase the proportion of patients started on OAC for stroke prevention.

IV. STUDY RATIONALE

Preliminary data from three Sentinel Data Partners between 1/1/2006 and 6/30/2015, identified 231,696 patients (1.4%) with at least 2 diagnoses of AF (ICD-9 codes of 427.31 or 427.32) over the study period, among 16.2 million covered lives. Within the 231,696 AF patients, there were 201,882 with a CHA₂DS₂-VASc score of 2 or greater (based on administrative claims data in the Sentinel Distributed Database), which is an American Heart Association (AHA)/American College of Cardiology (ACC) guideline indication for OAC. Over the study period from 2006 through 2015, 52% (n=105,256) patients filled at least one prescription for anticoagulation, meaning that 48% of patients with CHA₂DS₂-VASc score of 2 or greater never had a pharmacy claim submitted for an OAC during the study period. While there may be clinical or health system related reasons for not treating some of these patients, this apparent significant gap of guideline-based adherence is a public health issue of interest. The presented protocol is an opportunity to test the potential for developing and testing a health plan (Data Partner) based education intervention to improve the quality of care.

V. STUDY OBJECTIVES

A. PRIMARY OBJECTIVE

The primary objective is to evaluate the effect of the patient and provider education interventions (versus usual care with delayed provider education intervention) on the proportion of patients with evidence of at least one OAC prescription fill (defined as one OAC dispensing or 4 INR tests) over the course of the follow-up through the date on which at least 80% of eligible study participants have at least 12 months of follow-up time.

B. SECONDARY OBJECTIVE

The secondary objectives are to evaluate the impact on outcomes of the patient and provider education interventions over the course of the follow-up through the date on which at least 80% of eligible study participants have at least 12 months of follow-up time:

- 1. Incident rate of stroke or transient ischemic attack (TIA) hospitalization
- 2. Incident rate of hospitalization for stroke
- 3. Time to first OAC prescription fill
- 4. Proportion of days covered by OAC prescription fills

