- 5. Proportion of patients actively on OAC at 12 months of follow-up
- 6. Incident rate of hospitalization for any bleeding
- 7. All-cause in-hospital mortality rates
- 8. All-cause mortality rates among patients with accurate out-of-hospital mortality data (such as Medicare Advantage patients)
- 9. Health care utilization for AF patients, which would be reported as counts of number of health care utilization events (outpatient visits, days hospitalized, number of emergency department visits, etc.)

C. EXPLORATORY OBJECTIVES

The exploratory objectives are to:

- 1. Evaluate the effect of the early and delayed education interventions on primary and secondary endpoints over the course of the follow-up through the date on which at least 80% of eligible study participants have at least 24 months of follow-up time.
- 2. Explore the CTTI and the FDA supported Sentinel Data Partnership's ability to successfully conduct a pragmatic trial to answer important questions to improve public health.

VI. STUDY DESIGN AND DURATION

The study is a prospective, randomized, and open-label education intervention trial. Patients with AF and a CHA₂DS₂-VASc score of 2 or greater will be randomized in a 1:1 ratio to an early intervention cohort and a delayed intervention cohort within each participating health plan. The definition for OAC medication fill will be an OAC medication dispensing or at least 4 INR tests in the claims data.¹ The claims records of the patients randomized to the early intervention cohort will then be linked to "fresh" (i.e. about 1-4 months old) pharmacy claims data at the time of randomization. Patients without evidence of an OAC medication fill during the 12 months prior to randomization will be included in the patient-level and provider-level early educational intervention (patients randomized to this early intervention with evidence of an OAC medication fill during the 12 months prior to randomization will be excluded from the trial.). In addition to usual care, these patients and their providers² will receive a

¹Not all OAC dispensings are well captured in pharmacy claims, particularly, for warfarin. INR tests are assumed indicative of OAC fills that were not billed through the claims. 4 INR tests or values within a 12-month period will be used as a proxy since that is roughly the number of tests administered in the process of stabilizing dose.

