The providers of patients in the delayed cohort who did not receive OAC medication during the course of the 12-month study period and meet our inclusion criteria will receive the delayed intervention: the provider-only education intervention, a one-time mailing administered 12 months after at least 80% of early intervention mailing have occurred (patients will not receive any educational materials unless no provider can be identified for a mailing). We intend to assess the primary and secondary endpoints again once at least 80% of patients have at least 24 months of follow-up time to assess the durability and longer-term outcomes of the effect of the patient- and provider-level education intervention, as well as the use of OAC following the delayed provider-level education intervention. However, as this second assessment is exploratory, we may not conduct these analyses if the results of the primary outcome are null.

Because the Sentinel Distributed Database will be used for follow-up information, and this information is refreshed approximately quarterly and this is done on separate timetables for the different health plans, it is likely that when at least the required follow-up time is available for at least 80% of people, there will be more than 12 or 24 months of follow-up for over 80% of people. All participants' outcomes will be assessed using all possible person-time; patients will have different duration of follow-up and that will be accounted for in the analyses.

A schematic diagram below shows the design of the early intervention period of the study over the course of the follow-up through the date on which at least 80% of eligible study participants have at least 12 months of follow-up time:

^{*}Baseline characteristics of delayed and early intervention cohorts will be taken from the same time point at randomization from a dataset that is archived at randomization, while exclusion criteria for evidence of OAC medication fill or P2Y12 antagonist use was determined at randomization for the early intervention cohort and approximately 12 months post-randomization for the delayed intervention cohort.

[figure not shown]
For analysis, treatment status is at time of randomization or corresponding early intervention mailing; for the delayed intervention mailing it is prior to mailing.

^{**}All possible person-time will be used to assess participants' outcomes (patients will have different duration of follow-up).

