- The sample size has 80% power to detect a 0.5% absolute reduction in stroke, assuming a cumulative 1-year incidence of stroke of 4.2% in control (delayed intervention arm) patients and 3.7% in intervention (early intervention arm) patients. The assumption is that patients not on oral anticoagulation have an annual stroke rate of 5%, and stroke will be reduced by 50% (HR=0.5) in the treated (anticoagulated) population. The 80% power requires that 52% of early intervention arm patients are treated at 1-year as compared to 33% in the control arm.

B. POPULATIONS FOR ANALYSIS

All analyses will be based on a modified intention-to-treat principle (i.e., all identified early intervention patients who meet eligibility and are mailed the intervention will be included; using "pseudo" wave assignments, all identified delayed intervention patients who meet eligibility at the time of corresponding early mailings will be included in the analysis). The primary endpoint will be calculated based on the proportion of patients with evidence of at least one OAC prescription fill over the course of the follow-up through the date on which at least 80% of eligible study participants have at least 12 months of follow-up time. An as-randomized analysis will be performed for the primary endpoint as a sensitivity analysis. All possible person-time will be used to assess participants' outcomes; patients will have different duration of follow-up and that will be accounted for in the analyses. Patients will be censored from the analysis at the time of death, disenrollment from the health plan, loss of medical or pharmacy coverage, or change in eligibility for inclusion in research based on health plan membership. The statistical analysis plan (SAP) provided more information and outlines in detail how granular aggregate data will be received from each Data Partner in lieu of patient-level data.

XV. OUTCOME DEFINITIONS

All outcome definitions will be based on available claims data.

- 1. Evidence of OAC start: the proportion of AF patients who have at least 4 INR values measured or who fill at least one OAC prescription for apixaban, dabigatran, edoxaban, rivaroxaban, or warfarin over the course of the follow-up through the date on which at least 80% of eligible study participants have at least 12 months of follow-up time

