- Health care utilization, reported as counts of number of health care utilization events (outpatient visits, days hospitalized, number of emergency department visits, etc.)

Depending on the review of preliminary data, the primary endpoint and some secondary endpoints may be examined separately by warfarin and novel OAC. This will be descriptive only and will not include formal statistical testing.

C. EXPLORATORY ENDPOINTS

We will evaluate the effect of the early and delayed education interventions on the primary and secondary endpoints once at least 80% of eligible study participants have at least 24 months of follow-up time (the early intervention includes mailing to the patient and provider while the delayed intervention, at approximately 12 months follow-up, only includes a provider mailing). Note that we may

¹ Data for out of hospital mortality are not available

not conduct these analyses if the results of the primary outcome are null in the 12-month follow-up assessment. Therefore, this statistical analysis plan does not include the details of analyses for a 24-month assessment.

D. DATA SOURCE

The data used for the study are claims data from the five participating sites, transformed into the Sentinel Common Data Model. At the time of analysis, the data available in the Sentinel Distributed Database (i.e., those approved and in use for Sentinel routine surveillance activities) will be used to assess the primary and secondary endpoints.

As background, the identification and creation of the study cohort was based on the claims data in the Sentinel Distributed Database plus linked “fresh” data (i.e., about 1 month old) for pharmacy claims and enrollment information. The target population for the study was those members enrolled in the sites who did not have evidence of an OAC medication dispensing in the 12 months prior to randomization; the fresh and production data ensured we identified those eligible for the trial. The data used for routine Sentinel activities are several months old – hence the need for certain “fresh” data – and the date of the last available claims varies by site.

E. PATIENT INCLUSION CRITERIA

All inclusion and exclusion criteria were determined by claims data. For entry into the study, the following criteria **MUST** be met at the date of randomization:

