All possible person-time will be used to assess participants’ outcomes. For the time-to-event analysis, patients will be censored from the analysis at the time of death, disenrollment from the health plan, loss of medical or pharmacy coverage, or change in eligibility for inclusion in research based on health plan membership.

[figure not shown]
Providers may have more than 1 patient in the study – either within the same arm or in both the early and delayed intervention arms. The frequency of this, when provider overlap can be identified, will be reported descriptively and it is expected to be a low proportion of whole population. Depending on the number of patients in this scenario, a sensitivity analysis may be considered to examine the effect.

There were a few variations in the implementation of the early intervention across the Data Partners due to pragmatic issues. The intervention per the protocol is targeted at both member and provider (i.e., the provider who gave most recent AF diagnosis). If the AF provider was a facility in the source data, the educational intervention was applied to the member only, unless the site chose an alternate provider. In the latter case, the intervention was sent to both the member and the alternate provider. The number of patients in each of these variations to the intended intervention will be reported.

A detailed Consort flow diagram will be provided showing the number of patients randomized to the early and delayed intervention groups, the numbers of subjects lost to follow up or excluded from analyses, and the number of subjects evaluable for the key study endpoints (Figure 1).¹

All analyses will be conducted using SAS version 9.4 or higher software (SAS Institute Inc., Cary, NC). However, version and modules to be used could vary from one Data Partner to another. All tests will be two-sided and a p-value of <0.05 will be considered statistically significant. No multiplicity adjustment will be made.

Figure 1. Consort Flow Diagram

A. METHODS FOR ANALYSIS IN DISTRIBUTED DATA NETWORKS

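### Active OAC is defined at 12 months but analysed at the end of follow-up, and no rule stops the 12-month secondary analyses at the delayed provider mailing

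*SAP*

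**What the plan says.** **Active OAC.** Protocol V.B and SAP I.B list it at 12 months, and Protocol XV places it at the end of one-year follow-up. SAP II.D.3 compares it at the end of follow-up, with last observation carried forward if censored. Table 6 also limits the comparison to patients treated for at least one day, which II.D.3 does not say.

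**End of follow-up.** SAP I.A and I.B give a nominal calendar close: when 80% of eligible participants have reached 12 months. SAP II, however, states "All possible person-time will be used to assess" outcomes. SAP I.D takes its data from a moving source: "At the time of analysis, the data available in the Sentinel Distributed Database". SAP I.F expects more than 12 months for over 80% of patients. SAP II.D.4 and Tables 5, 7 and 9 refer to all follow-up.

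**Delayed mailing.** Protocol VI describes it as "a one-time mailing administered 12 months after at least 80% of early intervention mailing have occurred", so its trigger nearly coincides with the nominal close.

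**Censoring.** Protocol XIV.B reads "Patients will be censored from the analysis at the time of death, disenrollment from the health plan, loss of medical or pharmacy coverage". SAP II has a rule for time-to-event work only, in these words: "patients will be censored from the analysis at the time of death, disenrollment from the health plan, loss of medical or pharmacy coverage". Both add change in research eligibility. Neither names the delayed mailing.

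**Primary endpoint.** The logistic model (SAP II.C.1) is described both over 12 months and up to the 80% date. The Table 2a shell fixes 365 days. No sentence covers patients lost before day 365 without a fill.

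**The concern.** The active-OAC mismatch needs no assumption: endpoint and analysis refer to different days for most patients. Being read at one late time point, it is also the endpoint most exposed to anything that happens after month 12.

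On person-time, the letter's effect has its own place in the plan. Protocol V.C makes it exploratory: "Evaluate the effect of the early and delayed education interventions on primary and secondary endpoints over the course of the follow-up" to 24 months. SAP I.C says "this statistical analysis plan does not include the details of analyses for a 24-month assessment". If the Sentinel refresh used for the 12-month analysis runs past the mailing, an unstated part of that effect enters the 12-month results, in an amount set by refresh dates.

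On the primary endpoint, the design plans for 30% loss in a year, and SAP I.F promises that unequal follow-up will be accounted for. A plain logistic model cannot censor. Five Data Partners run the same distributed code, so the rule for early loss has to be written down.

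**Working it through.** **1. The plan's own figures.** From SAP I.G (18% untreated, 7% treated; uptake 33%, 38%, 40.5%):
- 0.18×0.67 + 0.07×0.33 = 14.37%
- 0.18×0.62 + 0.07×0.38 = 13.82%
- 0.18×0.595 + 0.07×0.405 = 13.545%

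With 40,000×0.70 = 28,000 per arm, two-proportion power is 46.4% and 80.4%, against the stated 46% and 80%. At 40.5% uptake the hazard ratio is ln(1−0.1354)/ln(1−0.1437) = 0.938.

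**2. Control time after the mailing.** Assumptions not in the documents: constant hazards, and a cut 3 or 6 months after the mailing (T = 15 or 18 months).
- Attrition hazard a = −ln(0.70) = 0.357 per year.
- Post-mailing share s = 1 − (1−e^(−a))/(1−e^(−aT/12)) = 0.166 (T = 15), 0.276 (T = 18).
- Only providers of untreated controls are mailed. At 67% untreated, 0.111 (0.185) of control time is affected.

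**3. Effect on stroke/TIA.** Let k be the mean fraction of the contrast that survives the mailing. Then f = (1−s) + s·k, HR = 0.938^f and z = z12·f/√(1−s), with z12 = 2.816 at 80.4% power and 1.870 at 46.4%.

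| Scenario | Cut +3 months | Cut +6 months |
|---|---|---|
| Letter adds the same uptake evenly over a year: k | 0.877 | 0.757 |
| HR; power (from 80%) | 0.939; 86% | 0.942; 87% |
| Contrast vanishes at once (k = 0): HR; power (from 80%) | 0.948; 73% | 0.955; 67% |
| k = 0 at 38% uptake: power (from 46%) | 40% | 36% |
| k below which power falls | 0.48 | 0.46 |

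The gradual k is the attrition-weighted mean of 1−u, with u the years since mailing. The last row solves f = √(1−s). The k = 0 case needs 7.5/67 = 11% of untreated controls to start on the mailing day.

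**4. Active OAC.** Suppose the 12-month contrast is steady and the letter closes it evenly over a year. Then 3/12 = 25% (6/12 = 50%) of it is gone by the cut. This treats a provider-only letter as equal to the patient-plus-provider mailing and uses all patients, not the Table 6 subset.

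**5. 365-day tables.** Post-mailing time can enter only for the up to 20% who start follow-up after the 80% date. Suppose these start 1 to 6 months late and move to the early-arm hazard (−ln 0.62) once mailed. The delayed-arm rate goes from 33.0% to 33.1–33.5%. For 6 months: 1 − exp(−(0.4005+0.4780)/2) = 35.55%, and 0.8×33% + 0.2×35.55% = 33.5%.

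**6. Loss before day 365 in the logistic model.** If lost patients count as non-starters, p_obs = h/(h+b)·(1−(1−p)(1−L)), with h = −ln(1−p) and b = −ln(1−L).
- Equal 30% loss: 28.1% vs 32.4%, OR 1.228. Full follow-up (33% vs 38%): OR 1.244.
- Illustration with no true effect (33% in both arms), early-arm loss 30%, delayed-arm loss 31% (32%):
  - Lost counted as non-starters: OR 1.009 (1.018), z = 0.55 (1.11) at 40,000 per arm, rejection rate about 9% (20%). At 20,000 per arm it is 7% (12%).
  - Event-free losses dropped, p_obs/(p_obs+(1−p)(1−L)): 37.5% early vs 37.6% (37.8%) delayed, OR 0.992 (0.984), the opposite direction.
  - Everyone lost before day 365 dropped: no bias, if loss is independent of starting.

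**The case against.** **Follow-up is meant to close before the mailing.** SAP I.A gives a calendar end, Protocol XVI.C dates database lock by the mailing trigger, and SAP I.F mails only to providers of patients untreated during follow-up. This is a fair reading, and it is why leakage cannot be called established. The design schematics may also mark a close that the text does not state. What remains is that the all-person-time wording and the expected overrun conflict with that close, and no censoring rule enforces it. Sentinel data also lag by several months, so a 6-month overrun is an assumption without documentary support.

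**The letter belongs to the comparator.** Protocol V.A describes the contrast as "versus usual care with delayed provider education intervention", so counting time under the assigned strategy is legitimate. That stands as a possible estimand, but it should be chosen and not left to refresh dates.

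**The harm is small, and a cut can cost power.** This stands: in the gradual scenario all person-time gives 86–87% power against 80% with the cut.

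**Active OAC is only loose wording.** Protocol XV does mix one-year follow-up with the end of the study period. The programmed analysis would still use a different day from the listed endpoint.

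**The primary is already covered.** Kaplan-Meier cumulative incidence for this endpoint (SAP II.D.1, Table 3) and a flow diagram of losses are planned. This largely stands, and only the counting rule is missing.

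A reader might go further and infer from SAP II that the arms will differ in attrition, so that the primary test has an inflated false-positive rate. The documents do not support this. That paragraph concerns invalid addresses, which act mainly through selection into the modified intention-to-treat set. The 9% and 20% figures illustrate one handling under assumed loss differences.

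**Conclusion.** The point holds in three parts of unequal weight.

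1. **Active OAC** is inconsistent as written, in its time point and in its Table 6 denominator. This rests on the text alone. The 25% (50%) loss of contrast is an illustration.
2. **Secondary analyses over all follow-up** have no enforced close at the delayed mailing. Contamination of the control arm is possible, and its likely effect on stroke/TIA is small: HR 0.938 to 0.939 (0.942) with a gradual letter. Power falls only if under about 48% (46%) of the contrast survives a 3 (6) month overrun. The cut date, letter effect and constant hazards are assumptions.
3. **The primary logistic model** lacks a counting rule for early loss. This is minor: equal loss barely moves the OR, and a true 5-point effect would still be found. With unequal loss, the size and direction of bias depend on the handling chosen.

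Nothing here shows that the primary comparison is invalid.

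**What to change.** (a) Read active OAC at 12 months from the wave or pseudo-wave date, or at the censor date if earlier, using the existing carry-forward rule. Reconcile the Table 6 denominator with SAP II.D.3.

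(b) For the 12-month secondary analyses in Tables 5, 7, 8 and 9, censor both arms administratively at each Data Partner's delayed-mailing date. Keep the all-person-time results as supportive.

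(c) State the primary window as day 365 in SAP II.C, and say how patients lost before then without a fill count in the logistic model. Read the planned Kaplan-Meier risk at day 365 (Table 3) beside the odds ratio. Inverse-probability-of-censoring weights are optional and would not repair the address-based selection that SAP II describes.

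The cost is SAP wording and one programmed censor date per Data Partner, settled before database lock. The price of (b) is some person-time after the mailing and possibly some power. The Kaplan-Meier risk assumes that loss is unrelated to starting OAC.
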